#### **5. HF-SMA at Providence VA Hospital:** The Providence VA instituted multi-disciplinary HF-SMA in 2011.

Patients are referred from inpatient and outpatient setting by their physicians. [name] oversees the HF-SMA in case of difficult patient scenarios. In preparation for this proposal, we abstracted data on 70 patients referred to this program: Mean age:  $75\pm12$  years, Caucasian (93%), 99% male, NYHA class 3 or 4 at baseline visit (66%), mean left ventricular ejection fraction of 42%, and 50% of patients takes  $>10$  prescribed medications. There was a mean of  $41\pm64$  days delay from hospital discharge to attendance of HF SMA. For care coordination, referral into telehealth occurred in 22% and for home care was 4%. Medication changes and dose titration occurred in 62% of patients. Preliminary results showed a 30-day readmission rate of 6% and a 180-day readmission rate of 25% for all patients enrolled in HF SMA. In contrast, data from the VA Inpatient Evaluation Center showed a HF readmission rate for Providence VA at 22% for 2013 and pilot data from a national sample of discharged HF patients ejection fraction  $<40\%$  showed a 180-day readmission rate of 40%, suggesting a possible reduction in rehospitalization rate by HF-SMAs.

Interview of patients showed that most patients would agree that HF-SMAs are helpful: *"I find it informational..different people have different ideas..last time I came in, one of the gentlemen that was having trouble with his ankles..socks a little too tight..then somebody says, then cut the top of the socks off..."* Medication reconciliation and adherence as well as diet counseling are two most frequently mentioned themes: *"Especially the medications, which I found out the hard way... 'cause I had stopped it...it got confusing to me, all the medications..."*; *"learn a lot about diet such as fat, salt and ice cream intake,... Send a cook-I don't know how to cook!"* We also learned that sometimes we give too much information to patients: *"...too much actually...I haven't read a book in like forty years..."* We also found out that at times we did not explain clearly why the patients are attending the HF SMAs: *"I don't remember it at all, so, that's why they ought to let people know what they're doing, exactly what they're there for, because I really wasn't sure why I was there.."* We also learned that patients within 1-2 weeks of hospital discharge are often too frail to want to attend SMAs and not eager to interact, so they often delay their appointment until 3-4 weeks out. These lessons helped us designed the current study to open the window of enrollment up to 12 weeks after their discharge.

Interview of physician stakeholders suggested that many physicians did not know about HF-SMAs or their patients attended HF-SMAs when referred by another provider. These observations taught us that communication with patient's physicians is important after the HF-SMAs for care coordination.

#### **6. HF-SMA at Phoenix VA Hospital:** The Phoenix VA instituted weekly HF-SMA in 2013 with capacity

to see 4-6 patients in each session. [name] oversees the HF-SMA in case of difficult patient scenarios. Data on 54 patients referred to this program showed a patient population with a median age of 66 years, 82% White, 100% male, with a mean left ventricular ejection fraction of 35%, and the median number of medications = 10. Preliminary results after SMA showed a 90-day readmission rate of 7% and mortality of 4%, which is in contrast to the 25% 30-day readmission rate for Phoenix patients with a recent HF discharge (FY2014).

Focus groups conducted with patients after HF SMA suggested that the patients liked the open forum format and they believed SMA helped because it addressed a broad spectrum of concerns, provided additional medical information and strategies for coping with illness, had more time to talk with healthcare team, explored questions more deeply/reflect on answers, the conversation-like setting and support group' environment ("Not alone") and the learning from other patients' questions/ experiences as well as opportunity to share own experiences. Among the concerns expressed, one patient expressed that others were judging him and inhibited his openness going forward and another patient expressed: *"Group providers and patients don't know me as well and not a safe environment to voice personal issues as they can be misconstrued"*; *"your personal doctor isn't there"*. These are important lessons learned to control group dynamics and avoid stigmatization, earn the trust and have guidelines for participation to protect privacy. Some patients needed clarification on whether SMA is meant to replace visits to doctors (possible misunderstanding among new SMA patients about

the role their SMA provider plays). In our current model, the patients are advised that all treatment plans are communicated back to their primary providers via CPRS (provider decision support).

Overall, the above data support the feasibility of SMAs in HF, experience of the team in RCTs and multi-site studies. However, the effectiveness of HF-SMA in improving patient outcomes is still unknown despite strong theoretical underpinnings, and further investigation is warranted.

## **C. STUDY DESIGN OR APPROACH**

**1. Overview** This will be an open-label multi-center randomized-controlled trial of parallel design, to study the effectiveness of HF SMA in improving the health status (Aim 1), hospitalization or mortality (Aim 2) of patients discharged from a HF hospitalization. In addition, we will study intermediate outcomes such as process measures of HF-self-care and a biological measure of clinical status (BNP levels) (Aim 3). Finally, we will conduct fidelity assessments and a pre-implementation evaluation through interviews with patients (and caregivers if available and willing) to determine satisfaction and possibilities of refinement of the HF SMA, and physician stakeholders to assess for potential barriers of implementation. We will enroll patients within 12 weeks of discharge from a HF admission and/or IV diuretic therapy, who will be randomized to receive either HF-SMA versus usual care. The conduct of the clinical trial will follow the suggested best practices in the conduct of randomized trials as published in the British Medical Journal. The study duration will be 180 days from the time of randomization. Both quantitative and qualitative methods will be utilized to assess the outcomes of this intervention. The HF-SMA will consist of four sessions of 2-hour duration that occur every other week for 8 weeks or based on the clinics' appointment availability.

### **2. Population**

Inclusion criteria: 1) All subjects >18 years old, 2) within 12 weeks of discharge from a hospitalization with a principal diagnosis of HF (ICD-9 codes in Appendix Table) and/or IV diuretic therapy, 3) able to participate in a group setting and 4) able to sign informed consent, will be eligible for enrollment. The study team will work with subjects with transportation problems to help resolve travel issues if needed using VA channels (e.g., identifying support persons to help, Veteran vans, Community-Based Outreach Clinics with shuttle transport to the main hospital, etc.) since in most cases, VA provides support for transportation for Veterans to attend clinic.

Exclusion criteria: We will exclude patients who are:

1) Unable to attend the group sessions due to either psychiatric instability (acutely suicidal, psychotic) or organic brain injury (e.g. severe dementia, encephalopathy) that precludes self-reporting on health status.

2) Discharged to hospice or nursing home facilities for long term care, or patients with a code status of comfort-measures-only since the setting and goals of disease management will be very different compared to the general HF patients after discharge, who are the target of our intervention.

3) Recipients of heart transplant or ventricular assist devices, patients receiving intravenous inotropic infusions for heart support, women who are pregnant, and patients with end-stage liver disease or renal disease on dialysis since these conditions would preclude them from standard HF care. All women of childbearing age will have a pregnancy test before study enrollment.

We will not exclude patients who are currently enrolled in HF education classes, support group or HF clinics, as these co-interventions are often present in optimal "usual care" and patients are often referred to SMA from these settings. In addition, it would be important to know the effectiveness of the SMA intervention, if any, in presence of potential co-interventions. We will account for co-interventions using stratified randomization, so equal proportion of patients participating in above-mentioned programs would be allocated to each study arm. It is possible that patients are referred in the middle of the study, for which we will track them carefully and accounted for them in the analysis plan.

For recruitment from the inpatient setting, we will partner with hospital's discharge planning staff to obtain a list of potential or soon to be discharged patients. Once eligibility is confirmed through medical record review, we will contact the potential participant's inpatient providers to ask for their permission to approach these patients. Once permission obtained, we will approach the patient while in the hospital with an information sheet and ask to contact them for the study after discharge. For recruitment in outpatient settings, once eligibility is confirmed, we will contact the potential participant's personal physicians to obtain permission to contact the patient. Once permission and endorsement is obtained, we will send a joint recruitment letter from the patient's personal provider along with the investigators that will include a return envelope with a response card to contact them for the study. In order to enhance participation and after permission from the IRB, we will send information material to discharge planning staff and place signage in each of the cardiac testing laboratories, rehab facilities, and cardiologist and primary care physicians' offices. Once contacted and agreeable, the patient will come for an initial study visit with the research assistant and informed consent will take place. Our preliminary data showed that in 2013, there were ~130 patients discharged with HF at Providence VAMC and ~250 patients at Phoenix VAMC; of which, we plan to annually recruit 50 and 75 patients in each site, respectively, over 36 months for a total of 375 patients.

**5. Randomization and retention:** Once enrolled, patients will be randomly assigned on a 1:1 ratio to intervention or placebo arms using a stratified block randomization method with block sizes of 4 in each site to ensure balance of the stratified variables. Stratification will be based on the study site and the presence or not of: a) co-intervention (enrollment to HF clinic, support group or education), b) ≤2 hospitalizations in the last 6 months, and c) left ventricular ejection fraction <40%. Randomization will be done by the call-in method to a central computer administered by the study coordinator at Providence VAMC, the coordinating site. To ensure subject safety and continuous engagement in study procedures, patients will be called by phone by study staff on a monthly basis following randomization to answer any questions that may arise, ask for participation in HF programs and doctor's visits, ER visits, document adverse events and maintain study engagement. Patients in the control arm will be invited to participate in HF-SMAs at the end of the study, to honor patient's preferences.

Our preliminary data showed that our recruitment in prior SMA research has been successful, ~50-60% of those screened and eligible agreed to enroll in SMAs; and then about 90% of those enrolled finished the study. Reasons for drop out are: geographic mobility, change in work schedule, incarceration, and homelessness. Yet, we have been able to maintain a good retention rate, through a combination of excellent relationships with participants, and a perceived value of the study to clients.

**6. HF-SMA:** The HF-SMA team includes a dietitian, a health psychologist, a nurse, and a nurse practitioner and/or a clinical pharmacist; one of which will lead the group discussions. Caregivers if available and willing, are allowed and encouraged to attend SMAs but NOT required, similar to how family members are allowed and encouraged to attend usual care clinic visits, but NOT required. Inadvertent loss of privacy is a concern in SMAs and we will clearly state that risk in the draft informed consent form (Appendix). At the beginning of each session the facilitator will provide SMA group guidelines for participation for the participants, caregivers and providers during the group interaction. Participants will be advised regarding appropriateness in sharing, as well as the expectations of privacy and confidentiality for patients and caregivers. Specifically, patients will not be asked to reveal any sensitive information about themselves and will be advised that the providers will not reveal any of the participants personal information during the group sessions. The SMA providers in both sites are very experienced and have been trained to respect privacy and avoid eliciting sensitive information. The session will start with an assessment of the patients and their needs followed by pre-assigned disease self-management education, followed by patient-initiated disease discussion, and conclude with break-out sessions of individualized behavioral intervention, medication reconciliation and case management by the multi-disciplinary team. The HF-SMA group will consist of 4-6 patients (and caregivers if present), of 2h duration broken down into:

1) **Patient intake** (10 min): they will complete a salt intake survey (appendix), blood pressure, heart rate, weight, leg /sacral edema, heart and lung sounds (nurse, pharmacist, and/or nurse practitioner).

They will also undergo medication reconciliation (10-15 minutes each patient): Clinical pharmacist or nurse practitioner reviews patients' medications against hospital discharge instructions and performs brief medication therapy management evaluation. In order to perform a thorough assessment of medications and adherence, we will ask the patient to bring all the medications in all HF-SMA visits (prescribed and non-

prescribed). This list of medications will be corroborated with electronic medical records and local pharmacy (if non-VA medication) during the education sessions, so no time is spent in waiting. The same will be done if patients informed that a change had occurred since discharge from the hospital, so that the current list can be corroborated against the medication list from physician's offices records.

2) **“Meet and Greet” and patient need assessment** (5 minutes, all team members). Patients are introduced to the team and to each other and are asked about self-care topics they would like to discuss.

3) **Group Education** (15-30 minutes): theme-based discussion based on curriculum published by the HF Society of America into 4 sessions:

a) Taking control of HF and Self-care: we will discuss the causes and types of HF, early detection of HF symptoms and how to monitor for signs of worsening (i.e. leg swelling, shortness of breath), when to call provider, daily weights, and VA resources to help them in disease monitoring such as telehealth.

b) How to follow a low-sodium diet: discussion of low and high sodium foods, read food labels, eating out, cooking tips, supermarket tips/tour, cooking demo and meal planning.

c) HF Medicines: HF medication types and how they work, adherence, pill boxes, side effects and when to report them, medications or foods to avoid, among other topics.

d) Managing Feelings about HF and advanced care planning: coping with negative emotions such as depression symptoms, family and caregiver support, recognizing anxiety and depression, when to seek medical help, advance care planning discussion with their physician and when to consider turning off defibrillators (this topic was suggested by a caregiver)

4) **Patient-initiated guided discussion** about HF self-care barriers (15-30 min)

5) **Individual break-out session** (45-60 min): patients rotate with providers depending on their needs for Individualized Self-Management and Support (15-20 minutes each patient): needs-based problem solving, e.g. clinical pharmacist or nurse practitioner if medication discrepancies are found or dose up titrations are needed. They can also meet with the nutritionist, psychologist, and/or nurse. Our experience suggests that the patient meets health care professionals of an average of 2 disciplines during the break-out sessions.

6) **Documentation:** chart documentation of the visit interventions will be performed by SMA team members. Communication of the treatment plan with the primary care provider and/or the cardiologist will be through electronic alerts in medical records and/or letter to non-VHA providers. Phone calls and/or encrypted emails will be used when clinically indicated.

7. Usual Care in HF: All patients will receive standard of care in HF as dictated by their cardiology physicians and primary care providers. It is highly encouraged that all patients see their physicians/health care providers within 14 days after their HF discharge. Physician follow-up after that may vary depending on the patient and physician, for which we will capture carefully through chart review and patient interview to compare attention given to patients in both arms of the study. In institutions such as Providence VAMC or Phoenix VAMC, patients are often referred to HF clinics (traditional one-to-one visits) with nurse practitioner for closer monitoring, which will be carefully tracked for analysis. This usual care arm will allow us to study the additive effects of HF-SMA and not in replacement of another intervention. In addition, there can be unexpected effects of active comparators in patient's outcomes as stated previously with interventions that have worsened rehospitalization risk. Therefore, a neutral standard of comparison such as usual care would be important. It will also allow the measurement of variation in effect size across different sites since usual care may vary.

8. Study Visits, Data Collection and Study Outcomes: There will be 3 research visits: 1) baseline for enrollment consent and data collection, and 2) at 90 days (+ or - 30 days) and 3) at 180 days (+ or - 30 days) after randomization for outcome collection, in addition to monthly phone calls in between study visits. All surveys will be self-administered unless the patient prefers otherwise. Only experienced interviewers will conduct the interviews, proficiency must be demonstrated to site PI. Training for the qualitative aspects of the study will be provided by the Cleveland site. All patient self-reported measures and interviews will be performed during the three research study visits. To accommodate patients, per request, study visits may be conducted over the phone or in a private location of their choosing with two study members present. Also to further accommodate patients, per request, de-identified surveys using only a study ID number may be mailed out along with a postage paid, self addressed return envelope. Patients will be instructed not to include their name on any of the returned surveys. Research assistants must demonstrate proficiency in data collection techniques to the site PI's.

Aim 1: Primary outcome is change in KCCQ and secondary is change in EQ5D.

Kansas City Cardiomyopathy Questionnaire (KCCQ)(Appendix): is a 23 item instrument validated in stable and decompensated HF patients with preserved or reduced ejection fraction. The questionnaire takes 4-6 minutes to complete, and reflects disease-specific health status over the prior two weeks. The domains of KCCQ are physical limitation, symptoms, self-efficacy, social limitation, and quality of life. The domains of the KCCQ have a high internal consistency with a Cronbach's alpha of 0.95 for the Overall Summary Score and  $\geq 0.62$  for all individual scales. The KCCQ has a significantly higher responsiveness to changes in health status than the Minnesota Living with Heart Failure Questionnaire and the SF-36. The overall summary score is 0-100 where higher score is better. The minimal clinically important change in survey score is 5 points, with a 10- and 20-point change reflecting moderate and large clinical changes, respectively. In the Eplerenone Post-AMI Heart Failure Efficacy and Survival Trial (EPHESUS), each 5-point decline in KCCQ Overall Summary Score on serial assessments was associated with a hazard ratio of 1.11 (95% CI, 1.05-1.17) for subsequent cardiovascular death or hospitalization. Preliminary data from Phoenix VA found a median Summary Score of  $52.4 \pm 27.8$  (n =32) in HF-SMA participants indicating fair/poor health status.

Overall health status (EQ5D) (Appendix): The EQ-5D is a well-known generic measure of health status. It has 5 questions that address five dimensions (mobility, self-care, usual activities, pain/discomfort, anxiety/depression) with five levels ranging from 'no problems' to 'extreme problems' each. Each health state (up to 3125) has a corresponding value reflecting references of the general population in various countries. Thus, the EQ5D can be summarized into an index value (utility) from 1 (full health) to 0 (dead) that can be used to calculate quality-adjusted-life-years in cost-utility analyses. The instrument takes only a few minutes to complete and is undemanding for self-completion. The EQ5D also contains a self-rated 20cm visual analogue scale (EQ VAS) ranging from 'best health you can imagine' to 'worse health you can imagine.' The EQ5D has moderate-strong convergent validity in relation to other measures of health-related quality of life as well as discriminative validity to detect clinical changes. However, it is less responsive to HF-related clinical changes than KCCQ. HF Studies reported strong correlation with disease severity in EQ-5D scores ranging from mean values of  $0.78 \pm 0.18$  in mild disease to  $0.51 \pm 0.21$  for severe disease.

Aim 2: Event outcomes (hospitalization or death) will be captured immediately after randomization. All events will be captured by monthly phone calls and chart reviews, as well as interview to study patients or caregivers during study visits. Copy of medical records for the reported hospitalizations, emergency room visits, or deaths will be obtained to confirm the event.

Aim 3: change from baseline in patient's HF Self-Care activities will be measured by HF Self-care Index and change in baseline BNP levels will be assessed through routine blood draw.

HF Self-Care - The HF Self-care Index (v.6)(Appendix): is a 22-item self-administered instrument composed of 3 scales: self-care maintenance, management, and confidence. It addresses diet, exercise, medication use, when to call the health provider, keeping doctor's appointments, weight monitoring, and recognition of change in health status or symptoms. Each scale is scored separately and has a range of 0-100. A score of  $\geq 70$  on each scale is considered adequate self-care, though benefit occurs at even lower levels. A score change of half standard deviation ( $\approx 8$  points) is considered a clinically relevant change. Pilot data from Phoenix VA showed low self-care scores in HF patients ( $64.9 \pm 19.9$ ) at baseline.

Plasma BNP levels: is a hormone released mainly by the heart in response to excessive stretching of heart muscle cells in cases such as HF. It is a test that is already being collected routinely in the clinical setting for HF patients. A cut-off of  $>100$  pg/mL in patients with new-onset dyspnea is suggestive of acute HF. It can also be used in outpatients after HF discharge to monitor for clinical deterioration and is highly predictive of death or rehospitalization, with a hazard ratio per unit increase of ln BNP of 1.84 (95% CI: 1.42 to 2.39). BNP provides clinicians with an objective and simple measure of the loading conditions of the heart.

Aim 4: Pre-implementation assessment.

1) Patients: We will conduct interviews of 20-25 patients in each study site who have undergone HF-SMA (with their caregivers if willing). Interviews will attend to patient (and caregiver) satisfaction and feedback on refinements for continuous quality improvement and determine, in what ways, the HF-SMA helped or did not help them feel better and/or avoid hospitalizations. We will strive for a maximum variation sampling of patients based on sociodemographic characteristics (age, women and minorities), number of co-existing conditions, social support and engagement during the sessions to achieve maximal thematic heterogeneity.

2) Stakeholders – Providers and administrators: We will interview ~10 physician stakeholders at each site, which will include primary care providers or cardiologists and one physician administrator (e.g. Chief of Cardiology, Medicine or Primary Care). We will purposefully select physicians who oversee HF patients who

participated in HF-SMA, and were interviewed, as part of the Aim 4 of the study. These will be informant interviews intended to provide insights on provider's perceived benefits of HF-SMA (any added value or detriment), and potential barriers for referrals. We will inquire specifically what type of patients, providers would refer to HF-SMA and what barriers may exist for them to incorporate this intervention into their referral practice.

**3) Formative Evaluation:** Will consist of fidelity assessment based on direct observation of HF-SMA. [name] [name] and his research staff will perform fidelity assessments for Providence VAMC, and through video-teleconferencing unit for Phoenix VAMC, in addition to two in-person site visits for direct observation as guided by the Fidelity sheet in Appendix. As an accompaniment to the fidelity assessment worksheet, we will also jot down explanatory field notes which will flesh out and provide depth to the assessment score. In line with field research best practices, raw records will be typed up within 36 hours to accompany the numerical scores, and this data—along with the interview data—will provide a rich and multi-sourced qualitative depth to the study. [name] [name] and his research staff will provide training on how to collect and record field notes. We will observe one HF-SMA session per site each month for 24 months to ensure fidelity.

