Sample Size and Power Considerations: The overall study sample will be 375 (225 patients from Phoenix VAMC and 150 patients from Providence VAMC). Statistical power for the aims 1 and 2 is estimated given these are the most relevant and the most restrictive in terms of power estimations. Under a conservative dropout rate of 15% for 180 days of follow-up for the main outcomes (Aims 1 and 2), we estimate the power with an effective sample size of 316 (15% less than the total sample) and a 2-sided significance level of 0.05 using nQUERY Advisor 7.0®. For aim 1, we assess the power to detect a clinically significant change in KCCQ of 5 points, assuming a baseline score of 63 (our preliminary studies), with a common standard deviation of 15 for the study arms, using a 2-sample t-test. For aim 2, we assess the power to detect a relevant decrease in rehospitalization or death risk of 25-30% at 180 days using a Cox Proportional Hazards model. Based on our preliminary data of 20,000 Veterans with ejection fraction <40% hospitalized with HF, their rehospitalization rates at 6 months is ~40%. Assuming similar event rates for rehospitalization or death, as shown in Table 2, we have good power to detect the proposed outcomes at very conservative estimates of effective sample size (n=158 in each arm, which is 85% of the total proposed recruitment target). Repeated measures at 90 and 180 days are also likely to add to the statistical power in Aim 1 to detect differences at the subgroup levels.

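### A single block size of 4, stated in an open-label protocol, could let staff who track a stratum know up to about a third of allocations in advance

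*Combined protocol and SAP*

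**What the plan says.** Section C, item 5 (Randomization and retention) specifies 1:1 allocation by a "stratified block randomization method with block sizes of 4 in each site". "Stratification will be based on the study site and the presence or not of" three binary factors: a heart failure co-intervention, two or fewer hospitalizations in the last six months, and ejection fraction below 40%. The strata therefore lie within site.

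On the mechanism, item 5 says: "Randomization will be done by the call-in method to a central computer administered by the study coordinator at Providence VAMC, the coordinating site". Item 4 lists Providence as one of the two recruiting sites. On the order of events, item 5 says: "Once enrolled, patients will be randomly assigned".

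Item 1 (Overview) states: "This will be an open-label multi-center randomized-controlled trial of parallel design". Past allocations can therefore be seen by staff.

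The available text does not mention varying the block size, keeping it from recruiting staff, or any other protection against prediction.

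**The concern.** In an open-label trial, hiding the list does not by itself conceal the next allocation. If the block size is constant and known, anyone who records earlier assignments in a stratum can work out the last one in every block, and sometimes the last two.

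The plan leaves room for that knowledge to affect who enters:

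- One inclusion criterion in item 2 (Population) is a judgement about whether the patient can take part in a group. An expected assignment to the group intervention could colour it.
- Eligibility review, approach and consent (item 4) all come before randomization. Allocating only after enrolment does not stop a prediction made earlier.
- The eligibility window is 12 weeks. The preliminary work at Providence reports that patients in the first week or two after discharge are often too frail to want to attend, so time of entry may be related to prognosis. Time since discharge is neither a stratification factor nor a named covariate.

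If patients enrolled when the group intervention is expected differ from those enrolled when usual care is expected, the arms differ before treatment. The primary outcome, KCCQ, is patient-reported and collected without blinding.

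**Working it through.** The plan states no predictability figure, so there is none to reproduce.

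**Inputs.** Block size 4, 1:1 ratio, and site by three binary factors, which gives 2 × 2 × 2 × 2 = 16 strata, 8 per site (item 5). Open-label (item 1). 375 patients, 225 at Phoenix and 150 at Providence (item 9).

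**Step 1: certain allocations in a complete block.** There are 6 equally likely blocks with two A and two B. AABB and BBAA each have 2 allocations that are certain from the earlier ones. ABAB, ABBA, BAAB and BABA each have 1. The mean is (2 × 2 + 4 × 1)/6 = 8/6 = 1.333 per block, and 1.333/4 = 33.3%. By position, the 1st and 2nd are never certain, the 3rd is certain in 1/3 of blocks, and the 4th is always certain.

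**Step 2: best guess.** The observer always guesses the arm that is behind and tosses a coin when the arms are level.

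- Position 1: 1/2.
- Position 2: 2/3.
- Position 3: 1/3 × 1 + 2/3 × 1/2 = 2/3.
- Position 4: 1.

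The sum is 2.833, and 2.833/4 = 70.8%.

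**Step 3: incomplete final blocks.** The mean stratum size is 375/16 = 23.4. Assume the leftover in a stratum is equally likely to be 0, 1, 2 or 3 patients, a mean of 1.5. Complete blocks give (23.44 − 1.5)/4 × 1.333 = 7.31 certain allocations per stratum. A leftover of 3 adds 1/4 × 1/3 = 0.08. The total is 7.40 × 16 = 118 patients, and 118/375 = 31.6%. Simulation under three assumed stratum mixes, from equal to very uneven, gives 118 to 119 patients (31.5% to 31.8%). Stratification therefore barely lowers the ceiling.

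**Step 4: effect of varying the block size.** This is a simulation of 24 patients per stratum, with sizes drawn at random with equal probability. The observer knows the set of sizes but not their order, and updates on every earlier allocation.

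| Block sizes | Certain | Best guess correct |
|---|---|---|
| 4 only | 33.3% | 70.8% |
| 4 and 6 | 5.9% | 68.6% |
| 4, 6 and 8 | 2.5% | 67.4% |

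A fixed, known block of 6 would give 25% and 68.3%. Varying the size therefore removes most of the certainty but little of the average guessability.

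**The case against.** The strongest case against is that one third is a ceiling. It needs staff who know the size and record every earlier allocation in the right one of eight strata at their site. Planned accrual is 50 a year at Providence and 75 at Phoenix. With equal strata (an assumption), that is 50/8 = 6.25 and 75/8 = 9.4 patients per stratum per year, or one about every 8.3 and 5.5 weeks. A 12-week window then spans only about 1.4 and 2.2 enrolments per stratum, which limits the scope for timing an entry. This stands as a reason to call the risk modest. It does not remove it, because so few patients are easy to log, and prediction can also affect whom to approach or judge suitable.

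Four stronger readings are tempting, and the documents do not support them:

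- A reader might infer that the resulting bias could be neither detected nor removed. Table 1 collects KCCQ, EQ-5D, self-care, PHQ-8 and BNP at baseline, and item 9 summarises baseline characteristics by arm and models KCCQ with baseline as a time point. Item 3 adds a registry of consenting decliners. Measured differences can be seen and partly adjusted for. Unmeasured ones, such as motivation, cannot.
- A reader might infer that staff control the timing of entry. Item 4 routes recruitment through provider permission and patient agreement, and the preliminary work says patients themselves often delay. Staff influence is possible but inferred.
- A reader might infer that recruiters were told the block size, or that the Providence coordinator recruits. The size is in the protocol, but the text does not say who could read it, and it gives the coordinator no recruiting role.
- A reader might infer that mixed sizes make block ends unidentifiable. Step 4 shows that about 6% of allocations stay certain if the set of sizes is known.

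**Conclusion.** The point holds as a design weakness with a cheap remedy. With one stated block size of 4 in an open-label trial, up to 33.3% of allocations could be known in advance in complete blocks, about 32% (some 118 of 375) with incomplete final blocks, and about 71% could be guessed correctly. These figures assume that staff know the size and track each stratum fully. The documents show neither that anyone did this nor that bias occurred, and fixed blocks with central call-in do not contradict anything else in the plan. Baseline data give partial protection, which does not extend to unmeasured factors.

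**What to change.** For all blocks not yet opened, use permuted blocks whose size varies at random within each stratum, for example 4 and 6. The study statistical analyst should generate the list. The sizes should be moved from the protocol to a restricted document and withheld from recruiting staff and from the Providence coordinator.

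Costs: a change in the list-generation code, and a possible end-of-stratum imbalance of 3 instead of 2. The coordinator would also have to administer the system without seeing the sizes. The project management plan describes the qualitative work as ongoing, so enrolment may have started. If so, a short amendment is needed, and it cannot undo what staff already know about blocks in use.

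If enrolment is complete, state the limitation and compare baseline characteristics by arm, including time since discharge, separately for predictable positions (every fourth, and a third that follows two like allocations) and unpredictable ones. This check is coarse. With about 118 predictable patients, 59 per arm, and the plan's SD of 15, the 95% interval for a baseline KCCQ difference is about ±1.96 × 15 × √(2/59) = ±5.4 points. A null result would not exclude a difference as large as the 5-point target.
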